████████ have a unique barbed design, which, theoretically, allows physicians to perform highly efficient continuous suture, and to improve operation efficiency. By reducing the operation time, the new product can achieve the same safety and effectiveness as compared with the interrupted suture technique [5, 7-10].

This study was designed to verify that ██████████ can improve the operation efficacy, can reduce the suturing and operation time as well as meet the clinical demand for suture safety, as compared to traditional interrupted suture technique during TKA surgery.

[figure not shown]

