#### **4.5.2 Determination of Sample Size**

The proposed sample size of 92 patients per arm (184 total) is considered adequate to test the hypothesis that [REDACTED] can reduce the time for incision closure compared to conventional sutures. Based upon a review of the literature, the mean incision closure time was assumed to be [REDACTED] minutes for conventional sutures, being calculated as a weighted (based on number of subjects) mean of the means observed in the studies reviewed. The studies reported incision closure times ranging between 14.4 to 26.5 minutes [5, 7-10]. It is expected that the [REDACTED] can reduce the incision closure time by [REDACTED] % compared to conventional sutures; therefore, the assumed mean closure time for [REDACTED] is [REDACTED] minutes. The standard deviations observed in the reviewed literature range from 3.43 to 8.5 minutes for the conventional sutures; the standard deviation for this study was conservatively assumed to be [REDACTED] minutes in both groups for several

reasons, such as the lack of data for [REDACTED] and that this patient sample may be older and with larger BMI. The distribution of incision closure time is assumed to be normal.

The statistical hypotheses for the primary endpoint are as follows:

- H0: Mean Barbed  $\geq$  Mean conventional suture tested against the alternative hypothesis
- Ha: Mean Barbed  $<$  Mean conventional suture;

Where:

- The assumed mean time to incision closure in conventional group is [REDACTED] minutes;
- The mean time to closure in [REDACTED] is [REDACTED] minutes;
- The assumed standard deviations in the two groups are both 8.

Based upon these assumptions, a total seventy seven (77) evaluable subjects per arm will achieve 90% power to detect a difference of [REDACTED] minutes (expected mean for [REDACTED] of [REDACTED] minutes and the conventional group of [REDACTED] minutes) with estimated group standard deviations of [REDACTED] using a one-sided two-sample t-test. The assumed one-sided significance level is 0.025.

If the higher limit of the one-sided 97.5% confidence interval for the difference in the Mean [REDACTED] time minus the Mean closure time for conventional suture is smaller than 0, then it will be concluded that [REDACTED] is considered to be superior to conventional suture. The sample size is adjusted to 92 per arm to account for a 16% withdraw rate [25-28].

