1.1.3 Other Objective(s)

The difference in the safety profiles for both wound closure procedures will be evaluated through the analysis of the incidence of wound complications including dehiscence, wound infections, and other adverse events.

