2.2 DEFINITIONS OF ANALYSIS SETS

There will be three analysis sets defined:

- Modified Intent-to-treat set (mITT set) consists of all randomized subjects who had the surgical incisions closed using the randomized suture
- Evaluable [or Per-Protocol (PP)] set consists of all mITT subjects who have no major protocol violations.
- Safety set consists of all subjects who receive surgery.

Major protocol deviations are deviations that have an impact on the primary endpoint, or that have an impact on the randomization assignment. These will be determined prior to database lock.

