3.3 SAFETY ANALYSIS

Safety variables include the incidence of SSI, ASEPSIS score (only for subjects with confirmed SSI), AIRE score, incidence of wound separation or dehiscence requiring intervention, incidence of delayed wound healing events, incidence of AEs and SAEs associated with wound closure.

All safety endpoints (see section 1.2.3) will be summarized descriptively by treatment group for the Safety analysis set using available data. There will be no missing data imputation for the safety analysis. The continuous variables including ASEPSIS total score (ranging from 0 to 100), and AIRE total score (ranging from 0 to 12) calculated as the sum

of individual scores for Erythema, Oedema, Pain and Temperature, will be summarized descriptively by number of subjects, mean, standard deviation, minimum, and maximum. Categorical data including the incidence of SSI, incidence of wound separation or dehiscence requiring intervention, incidence of delayed wound healing events, incidence of AEs and SAEs associated with wound closure will be summarized descriptively by frequencies along with the associated percentages. No inferential statistics will be generated for the safety endpoints.

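### The safety difference that the trial sets out to evaluate has no planned estimate and no measure of precision

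*SAP*

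**What the plan says.** The objective is a comparison. SAP 1.1.3 states that "The difference in the safety profiles for both wound closure procedures will be evaluated", by way of the incidence of wound complications, and Protocol 2.0 and the synopsis carry the same aim. Protocol 1.1 adds that the study was designed to verify that the device "can reduce the suturing and operation time as well as meet the clinical demand for suture safety", relative to interrupted suturing.

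The planned output is not a comparison. SAP 3.3 gives counts and percentages by treatment group for surgical site infection, dehiscence, delayed healing and wound-closure adverse events, and then says "No inferential statistics will be generated for the safety endpoints". Protocol 4.5.5 has the same sentence, and the statistical methods in the synopsis have its equivalent for the secondary safety endpoints. SAP 3.3.5 plans no further safety analysis. The only confidence interval in either document is the one for closure time (Protocol 4.5.4, SAP 3.2.1.1).

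On the population, SAP 2.2 says "Safety set consists of all subjects who receive surgery". It does not say whether those patients are grouped by the suture assigned or by the suture used.

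**The concern.** An objective framed as a difference needs an estimate of that difference and some indication of how well it is known. Two columns of percentages supply neither. Wound events may be few in a trial of this size, and when they are, the percentages alone say little about what size of excess remains compatible with the data. The point has some weight here because Protocol 1.1 presents suture safety as part of what the study should verify, and describes surgical site infection after knee arthroplasty as potentially catastrophic. A saving in closure time is worth less if wound safety is given up for it.

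The sentence in SAP 3.3 does not name confidence intervals. Its natural reading covers them, because the plan's own inference on the primary endpoint is a confidence interval.

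**Working it through.** **The plan's own figure.** Protocol 4.5.2 states that "a total seventy seven (77) evaluable subjects per arm will achieve 90% power", then "The sample size is adjusted to 92 per arm to account for a 16% withdraw rate". Dividing, 77 / (1 − 0.16) = 91.7, which rounds up to 92, so the figure reproduces. It rests on closure time alone. With "The assumed one-sided significance level is 0.025" and the stated SD of 8, the normal approximation gives a detectable difference of (1.960 + 1.282) × 8 × √(2/77) = 4.18 minutes (4.21 with the t distribution). The plan's own difference is blacked out, so this value is back-solved. No wound-event rate, safety margin or precision statement enters the sample size.

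**Inputs for the safety check.** From the documents: 92 per arm randomised, 77 per arm after the allowed withdrawal, 1:1 allocation. Assumed, because the documents give no rates: 0 to 3 events per arm.

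**Method.** For x events in n patients, with p = x/n and z = 1.96, the Wilson limits are

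[p + z²/2n ± z√(p(1−p)/n + z²/4n²)] / (1 + z²/n).

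With Wilson limits (l₁, u₁) and (l₂, u₂) and d = p₁ − p₂, the Newcombe limits are

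lower = d − √[(p₁ − l₁)² + (u₂ − p₂)²], upper = d + √[(u₁ − p₁)² + (p₂ − l₂)²].

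**0 v 0 at 92 per arm.** The Wilson upper limit is z²/(n + z²) = 3.8415/95.8415 = 0.0401, so the difference has limits ±4.0 points. At 77 per arm it is 3.8415/80.8415 = 0.0475, or ±4.8 points.

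**2 v 2 at 92 per arm.** p = 0.0217 with Wilson limits 0.0060 and 0.0758. Then √[(0.0217 − 0.0060)² + (0.0758 − 0.0217)²] = 0.0563, or ±5.6 points.

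The other cases, in percentage points (first count minus second):

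| Events | 92 per arm | 77 per arm |
|---|---|---|
| 0 v 0 | −4.01 to +4.01 | −4.75 to +4.75 |
| 1 v 0 | −3.02 to +5.90 | −3.57 to +7.00 |
| 1 v 1 | −4.90 to +4.90 | −5.80 to +5.80 |
| 2 v 0 | −2.13 to +7.58 | −2.51 to +8.98 |
| 2 v 2 | −5.63 to +5.63 | −6.66 to +6.66 |
| 3 v 1 | −3.10 to +8.13 | −3.65 to +9.62 |
| 3 v 3 | −6.27 to +6.27 | −7.40 to +7.40 |

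Miettinen-Nurminen limits agree with these within 0.3 point. For one arm, the exact two-sided 95% upper limit for 0/92 is 1 − 0.025^(1/92) = 3.9%.

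**How likely a blank table is.** For a single endpoint with the same true rate in both arms, the chance of no event in 184 patients is 0.995^184 = 0.398 at 0.5%, 0.99^184 = 0.157 at 1% and 0.98^184 = 0.024 at 2%. These rates are assumptions.

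**The case against.** The strongest reply is that the plan is consistent and conventional. Inference is reserved for closure time. Secondary efficacy is also descriptive only (Protocol 4.5.4, SAP 3.2.2), and SAP 2.4 treats all secondary endpoints as supportive. The SAP files safety under other objectives and says that the difference will be evaluated through incidence, which incidence by arm arguably delivers. Anyone can compute an interval from the published counts, and the table shells are in a separate document not available here. This stands to the extent that descriptive safety reporting is not a mistake in itself and no information is lost.

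A reader might infer more: that the plan will present few or no events as equal safety. The documents do not support that. They contain no equivalence or non-inferiority margin for safety and no decision rule other than the one for closure time. The sentence in Protocol 1.1 about achieving the same safety cites published studies and is not a planned conclusion. How readers would take 0% against 0% is a forecast.

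Two limits on the figures also stand. All event counts are assumed. And few events may not hold for the adverse-event endpoint, since an AIRE score above 1 must itself be reported as an adverse event (Protocol 2.3, SAP 1.2.3). Power for a safety test has no bearing here, because no test is proposed.

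What remains is that the objective names a difference and neither document plans to estimate it.

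**Conclusion.** The point holds as a mismatch between objective and analysis, and correcting it is a worthwhile, inexpensive improvement. It does not invalidate the plan and does not touch the primary analysis. If each arm has the same count of 0 to 2 events among about 92 patients, differences of about 4.0 to 5.6 points either way remain compatible with the data. Unequal counts or fewer patients widen this. The range depends on assumed counts and on a Safety set close to the number randomised. The documents state no clinically important excess, so whether 4 to 6 points matters is a judgement they leave open.

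**What to change.** In the synopsis (statistical methods), Protocol 4.5.5 and SAP 3.3, replace the sentence that excludes inferential statistics. All three must change together, or the documents will contradict each other. Suggested content:

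- For surgical site infection, wound separation or dehiscence needing intervention, delayed wound healing, and wound-closure adverse events and serious adverse events, report the between-arm risk difference with a two-sided 95% Newcombe confidence interval on the Safety set.
- State in SAP 2.2 how Safety-set patients are assigned to arms (as randomised or as treated), since a difference between arms depends on it.
- Label the intervals as estimation, with no hypothesis test and no multiplicity adjustment.
- State that the trial is not sized to show equal safety, and that absence of an observed difference will not be reported as equivalence.

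The cost is a small protocol and SAP edit and a few table columns. No patients are added and alpha is unaffected. The one drawback is that several unadjusted intervals could be read as tests, so the labelling needs to be explicit.

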3.3.1 Extent of Exposure

The descriptive statistics will be provided for subject follow-up time.

Follow-up time in days will be derived from the following formula:

Follow-up Time (days) = (date of last visit) – (date of randomization) + 1;

3.3.2 Adverse Events

An AE is defined as any untoward medical occurrence, regardless of its relationship to the study device (study suture) or the study procedure (TKA), which includes any new, undesirable medical experience or worsening of a pre-existing condition, which occurs at any point from the surgery to Final Visit.

The adverse event verbatim descriptions (investigator terms from the CRF) will be classified into medical terminology using MedDRA 20.0 or higher Version. Adverse events will be coded to primary System Organ Class (SOC) and PT using MedDRA (Version 20.0 or higher). All AEs will be summarized by treatment group. The incidence of AEs will be reported as the frequencies (percentages) of subjects with AEs within SOC and PT. Subjects will be counted only once within a SOC and PT, even if the subject experienced more than one TEAE within a specific SOC and PT. The frequencies (percentages) of subjects with AEs will also be summarized by maximum severity (mild, moderate, or severe), relationship to the study device and outcome.

All AEs will be presented in subject data listings.

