2. Use Acute Inflammatory Response Evaluation (AIRE) score measuring inflammatory tissue reaction. Of note, an AE will be reported when the score is >1. Refer to Table 3;
3. Incidence of wound separation or dehiscence requiring intervention;
4. Incidence of delayed wound healing events;
5. Incidence of wound closure related adverse events and serious adverse events;

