#### **4.5.5 Analysis of Secondary Safety Endpoints**

The incidence of adverse events (AEs) will be assessed at the preferred term level using the Medical Dictionary for Regulatory Activities (MedDRA) for event categorization. Incidence of AEs will also be assessed by 1) onset time (intraoperative or postoperative); 2) by relationship to study surgical procedure; 3) by relationship to the; and 4) by severity.

All safety endpoints (see section 2.2) will be summarized descriptively by treatment group for the Safety analysis set using available data. There will be no missing data imputation for the safety analysis. The continuous variables will be summarized descriptively by number of subjects, mean, standard deviation, minimum, and maximum. Categorical data will be summarized descriptively by frequencies along with the associated percentages. No inferential statistics will be generated for the safety endpoints.

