#### **6.1.3 Adverse Event**

An AE is defined as any untoward medical occurrence, regardless of its relationship to the study device (study suture) or the study procedure (TKA). An untoward medical occurrence includes any new, undesirable medical experience or worsening of a pre-existing condition, which occurs at any point from the surgery to Final Visit.

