#### **6.1.9 Relationship of Adverse Events**

It is the Investigator's responsibility to assess the relationship of an AE to the study procedure (TKA) and study device.

The following guidelines should be used in determining the relationship of an adverse event to the study device, study procedure, or other causality:

- **NOT RELATED:** The event is due to extraneous causes.
- **POSSIBLY RELATED:** The event is unlikely associated, but cannot be ruled out with certainty.
- **PROBABLY RELATED:** The event is likely associated, but another cause cannot be ruled out with certainty.
- **DEFINITELY RELATED:** The event is associated with a high degree of certainty; or
- **UNKNOWN:** The event cannot be defined by the categories listed above.

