## **7.0 Product Complaints**

### **7.1 Product Complaints Definition**

A product complaint is defined as any written, electronic or oral communication that alleges

deficiencies related to the identity, labeling, quality, durability, reliability, safety, effectiveness, or performance of a device (i.e., Barbed suture) after it is release for distribution (policy of Johnson and Johnson Medical Device Quality management). A product complaint may or may not be associated with an AE/SAE.

Product complaints may include, but are not limited to:

- a) Product contamination;
- b) Defective components;
- c) Poor packaging or product mix-up;
- d) Device malfunction, which is the failure of a device to perform as intended for this study;
- e) Labeling concerns
- f) User errors.

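### The endpoint of AEs and SAEs associated with wound closure has no derivation that is clearly the same in both arms, and the SAP omits two AE tables that the protocol planned

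*SAP*

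**What the plan says.** **The endpoint.** Protocol 2.3 lists "Incidence of wound closure related adverse events and serious adverse events", and SAP 1.2.3 repeats it. SAP 3.3 commits to reporting it by treatment group on the Safety set: "incidence of AEs and SAEs associated with wound closure will be summarized descriptively by frequencies along with the associated percentages". Neither document gives a rule for deciding that an AE is closure-related.

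**The causality fields.** Under Protocol 6.1.9 the investigator must "assess the relationship of an AE to the study procedure (TKA) and study device". There are five grades: not, possibly, probably and definitely related, and unknown. Possibly related is defined as "The event is unlikely associated, but cannot be ruled out with certainty". No text says which grades count as associated.

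**The meaning of study device.** Protocol 6.1.3 defines an AE "regardless of its relationship to the study device (study suture) or the study procedure (TKA"), and SAP 3.3.2 uses the same gloss. Protocol 7.1, on complaints, speaks of the "performance of a device (i.e., Barbed suture"). The Study Product line in the synopsis and the device description in Protocol 1.2 cover only the barbed product.

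**The AE tables.** Protocol 4.5.5 plans AE incidence by onset time, "by relationship to study surgical procedure", by a further relationship whose object is blank in the public text, and by severity. SAP 3.3.2 has AEs "summarized by maximum severity (mild, moderate, or severe), relationship to the study device and outcome". SAP section 5 reports no changes to the planned analyses.

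**The concern.** The safety objective is a comparison of two closure methods, so a closure-related event should be identified in the same way whichever method was used. Neither causality target is wound closure. If a site takes the study device to be the barbed suture, a stitch abscess in the barbed arm can be coded to the device. The same abscess in the control arm can be coded only to the TKA or to nothing. The count would then differ between arms for a reason unrelated to safety.

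The rating is also open-label. Protocol 3.3.2 states that the implanting surgeon and the medical records are not blinded, and the documents describe no blinded adjudication of AEs.

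The other wound endpoints do not fully stand in for this one. The SSI definition excludes stitch abscess. The separation endpoint covers only events that need intervention. Delayed healing is not defined. Minor separation, stitch abscess and adhesive reactions therefore have no assured wound endpoint other than this one.

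**Working it through.** The documents give no expected rate for closure-related AEs, so there is no stated figure to reproduce. The check is mainly a comparison of text, followed by an illustration of size.

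**Step 1: what the device field covers.**

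| Place | What it suggests |
|---|---|
| Protocol 6.1.3, SAP 3.3.2 | Study suture; could be either arm's suture |
| Protocol synopsis (Study Product), 1.2, 7.1 | Barbed suture only |
| Protocol 7.2 | Barbed suture, TSA and traditional suture, but for product complaints |
| Protocol 3.4.3.2, Table 5 | Control products also called devices, but not study device |
| Protocol 5.0 | Study suture and TSA named as separate items |

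The term is ambiguous. Protocol 3.3.1 also gives both arms an intradermal suture and a TSA, and neither product is expressly placed under either causality target. Even if the term means the assigned suture, events from these shared products have no stated home.

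**Step 2: what an analyst could do with the two fields.**
- Count device-related AEs only. This differs by arm if sites use the barbed-only reading.
- Count AEs related to device or procedure. This is symmetric, but it brings in events of the arthroplasty that have nothing to do with closure.
- Select events by clinical review of terms. This could work, but no list or process is stated.

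The text does not choose among these, and each choice leaves open which grades count.

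**Step 3: protocol tables against SAP tables.**

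| AE breakdown | Protocol 4.5.5 | SAP 3.3.2 |
|---|---|---|
| Onset time | Yes | No |
| Relationship to surgical procedure | Yes | No |
| Relationship to study device | Object blank in public text | Yes |
| Severity | Yes | Yes (maximum) |
| Outcome | No | Yes |

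The blank is treated as possible redaction and is not counted as an error. The two omitted tables are not declared in SAP section 5. The procedure table is where control-arm closure events would show if sites coded them to the TKA.

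**Step 4: illustrative size.** Inputs:
- n = 92 per arm (Protocol 4.5.2; 77/(1 − 0.16) = 91.7, rounded up to 92).
- p, the true closure-related AE rate, equal in both arms. Assumed at 5% and 10%.
- f, the share of control-arm closure events that can be coded to the study device. Assumed at 0, 0.5 and 1.
- All barbed-arm closure events are assumed to be coded to the device.

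Barbed count = 92 × p. Control count = 92 × p × f. Spurious difference = p × (1 − f).

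| p | f | Barbed | Control recorded | Spurious difference |
|---|---|---|---|---|
| 5% | 0 | 4.6 | 0 | 5 points |
| 5% | 0.5 | 4.6 | 2.3 | 2.5 points |
| 5% | 1 | 4.6 | 4.6 | 0 |
| 10% | 0 | 9.2 | 0 | 10 points |
| 10% | 0.5 | 9.2 | 4.6 | 5 points |
| 10% | 1 | 9.2 | 9.2 | 0 |

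In this illustration the difference goes against the barbed arm. With about 8 sites, the reading, and so f, may vary by site.

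**The case against.** The strongest reply is that the AE sections themselves gloss the term as the study suture. If that means whichever suture was assigned, the field works in both arms and the spurious difference from this source is 0. The clearest barbed-only wording, in Protocol 7.1, sits in a complaints definition, and 7.2 then covers the traditional suture as well. This stands: barbed-only is a supported inference, not the documents' definition.

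A reader might infer that control-arm closure events disappear from the safety report. The documents do not support that. SAP 3.3.2 tabulates all AEs by arm, SOC and PT whatever the causality, and lists them. SAP 3.3.2.1 does the same for SAEs. SAP 3.3 reports SSI, dehiscence requiring intervention and delayed healing by arm without any suture attribution. A reported stitch abscess would be in the PT table.

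A reader might also infer that the SAP has no closure-related table. It has one in SAP 3.3; what is missing is the rule for filling it. The eCRF and the table shells, which SAP section 7 places in a separate document, are not available and may contain such a rule. The rule would still belong in the SAP text.

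Finally, the loose definition of possibly related applies equally in both arms and creates no asymmetry by itself, and surgeon unblinding is disclosed as unavoidable. Both points are fair. They leave in place the missing derivation, the unplaced shared products and the two undeclared omissions.

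**Conclusion.** The concern holds in a limited form. The endpoint has no derivation that is clearly the same in both arms. It rests on an ambiguous field, rated by investigators who can know the arm, and two tables planned in the protocol are absent from the SAP without being declared. Any under-count of control events would be confined to the device-relatedness table and to this endpoint, and the mechanism in step 4 operates only where sites take the barbed-only reading.

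The size cannot be known from the documents. Under assumed equal rates of 5% to 10%, it lies between 0 and 5 to 10 percentage points; the upper end is a worst case in which no control event is coded to the device. No significance test should be attached to these figures, because SAP 3.3 plans no inference on safety. The primary endpoint, the sample size and the error rate are unaffected.

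**What to change.** 1. In Protocol 6.1.9 and the AE eCRF, add a rating of relationship to wound closure, meaning any suture or TSA used, with identical wording in both arms. If the eCRF can no longer change, define study device as the closure products used in each arm.
2. In SAP 3.3, state which causality grades count as associated with wound closure, including how unknown is handled.
3. Add, as a supportive count, a list of MedDRA wound terms fixed before database lock and counted regardless of causality. Stitch abscess, suture-related complication and wound discharge are examples. It overlaps partly with the existing wound endpoints and supplements the causality-based endpoint; it does not replace it.
4. Restore the tables by relationship to the surgical procedure and by onset time, or declare their removal in SAP section 5.

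The cost is SAP wording, one term list, a few extra tables and, where still possible, one eCRF question. The term count will include some events caused by the arthroplasty itself, in both arms.
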